3. DESCRIPTION OF DESIGN AND TRIAL POPULATION

3.1 OVERALL TRIAL DESIGN AND PLAN

This is a multi-centre, multi-national, prospective, randomised, double-blind, parallel-group clinical trial to investigate the efficacy and safety of nintedanib when co-administered with sildenafil, compared to treatment with nintedanib alone, in patients with IPF and advanced lung function impairment.

A total of approximately 250 patients will be randomised in a blinded fashion to nintedanib 150 mg bid co-administered with sildenafil 20 mg tid or to nintedanib 150 mg bid co-administered with placebo matching sildenafil. Patients will be stratified at randomization by the presence of any echocardiographic signs indicative of right heart dysfunction including right ventricular hypertrophy and right ventricular or atrial dilatation (as described in [sections 6.2.1](#) and [7.6](#)). Randomized treatment will last 24 weeks. During the randomized treatment period, dose reductions and/or temporary interruptions of nintedanib, as well as drug interruption of sildenafil/matching placebo, are allowed to manage adverse events ([section 4.2.1](#)). The planned follow-up period for patients after study treatment completion will be four weeks. Patients who prematurely discontinue all study drugs, will be invited to attend all visits as planned until week 24 (visit 7).

Each patient's participation in the trial is estimated to last approximately 32 weeks (from visit 1).

[figure not shown]

Figure 3.1:1 Trial design scheme

3.1.1 Administrative structure of the trial

The sponsor of this trial is Boehringer Ingelheim (BI).

BI has appointed a Trial Clinical Monitor, responsible for coordinating all required activities, in order to

- manage the trial in accordance with applicable regulations and internal SOPs,
- direct the clinical trial team in the preparation, conduct, and reporting of the trial,
- ensure appropriate training and information of local clinical monitors (CML), Clinical Research Associates (CRAs), and Investigators of participating countries.

Data Management, Pharmacokinetic and Statistical Evaluation will be done by BI according to BI SOPs.

Tasks and functions assigned in order to organise, manage, and evaluate the trial will be defined according to BI SOPs. A list of responsible persons and relevant local information can be found in the ISF.

Additional information for Japan only: A list of responsible persons and relevant local information (as protocol reference, if applicable) can be found in the ISF.

A Coordinating Investigator will be nominated and will be responsible to coordinate Investigators at different centres participating in this multicentre trial. Tasks and responsibilities will be defined in a contract. Relevant documentation on the participating (Principal) Investigators and other important participants, including their curricula vitae, will be filed in the ISF.

Sites selected for participation will consist of specialized referral centres experienced in the management of IPF.

A DMC, independent of the sponsor, will be established to assess the progress of the clinical trial, including an unblinded safety assessment at specified intervals, and to recommend to the sponsor whether to continue, modify, or stop the trial. Measures are in place to ensure blinding of the sponsor and all other trial participants.

All death cases will be assessed (to evaluate the primary cause of death), as well as all adverse events categorized as major adverse cardiovascular events (MACE) and all acute IPF exacerbations (based on written clinical reports, for diagnostic confirmation) by an independent Adjudication Committee (AC), in a blinded manner before data base lock. The tasks and responsibilities of the DMC and the AC will be specified in a charter.

The DMC and the AC will maintain written records of all its meetings.

A central laboratory will perform all protocol specified blood analysis of the trial.

An IRT will perform randomization of patients and ensure appropriate distribution of trial medication to sites during the trial.

A central vendor will provide spirometers for the complete duration of the trial.

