### **7.8.1 Adverse events**

Unless otherwise specified, analyses of adverse events will be descriptive in nature and will be based on BI standards (6). No hypothesis testing is planned. All analyses of AEs will be based on the number of patients with AEs and NOT on the number of AEs.

Furthermore, for analysis of AE attributes such as duration, severity, etc. multiple AE occurrence data on the CRF, will be collapsed into AE episodes provided that all of the following applies:

- The same MedDRA lowest level term was reported for the occurrences
- The occurrences were time-overlapping or time-adjacent (time-adjacency of 2 occurrences is given if the second occurrence started on the same day or on the day after the end of the first occurrence)
- Treatment did not change between the onset of the occurrences OR treatment changed between the onset of the occurrences, but no deterioration was observed for the later occurrence

For further details on summarization of AE data, please refer to the guideline “Analysis and Presentation of Adverse Event Data from Clinical Trials” (6).

The analysis of adverse events will be based on the concept of treatment emergent adverse events. That means that all adverse events occurring between first drug intake until 28 days after last drug intake (end of the residual effect period) will be assigned to the randomised treatment. Adverse events that start before first drug intake and deteriorate under treatment will also be considered as ‘treatment-emergent’.

All adverse events occurring before first drug intake and do not deteriorate under treatment will be assigned to ‘screening’ or ‘post-randomisation’ and all adverse events occurring after last drug intake will be assigned to ‘residual effect period’, ‘post-study’ or ‘follow-up’ (for listings only). Also, all AEs occurring between the start of an interruption and the end of interruption will be assigned to ‘off-treatment’ period in the listings. For details on the treatment definition, see [Section 6.1](#).

According to ICH E3 (7), AEs classified as ‘other significant’ will include those non-serious and non-significant adverse events which

- represents a marked hematological or other laboratory abnormality;
- led to an intervention, including withdrawal of drug treatment, dose reduction (‘action taken = discontinuation’ or ‘action taken = reduced’ for any of the study treatments), or significant additional concomitant therapy.

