In addition, the number of treatment emergent MACE events will be displayed including result of adjudication overall and by presence (yes/no) of signs indicative of right heart dysfunction.

The following adverse event groupings have been defined outside the trial protocol:

Table 7.8.1: 1 Adverse events by system using aggregated terms

System	Safety Topic	Definition (selection criteria)
Gastro-intestinal	Diarrhoea	PT Diarrhoea
	Nausea	PT Nausea
	Vomiting	PT Vomiting
	Abdominal pain	HLT 'Gastrointestinal and abdominal pains (excl oral and throat)
	Pancreatitis	SMQ Acute pancreatitis (narrow)
	Gastrointestinal perforation	SMQ Gastrointestinal perforation (narrow)
Hepato-biliary	Drug-induced liver injury (DILI)	PT Drug-induced liver injury
	Hepatic disorders combined	Table to show cumulative row for all 4 SMQs below, followed by a cumulative row for each subSMQ, followed by all PTs driving that subSMQ  SMQ Drug related hepatic disorders – comprehensive search (narrow) OR SMQ Liver related investigations, signs and symptoms (broad) OR SMQ Cholestasis and jaundice of hepatic origin (narrow) OR SMQ Hepatitis, non-infectious (narrow)
	Hepatic failure	SMQ Hepatic failure, fibrosis and cirrhosis and other liver damage-related conditions (narrow)
Cardio-vascular	Arterial thromboembolism	SMQ Embolic and thrombotic events, arterial (narrow)
	Myocardial infarction	SMQ Myocardial infarction (narrow)

Table 7.8.1: 1 Adverse events by system using aggregated terms (continued)

System	Safety Topic	Definition (selection criteria)
Cardio-vascular	Stroke	Pharmacovigilance Endpoint Stroke PTs (see list in ADS Plan)
	Haemorrhagic stroke	SMQ Haemorrhagic central nervous system vascular conditions (narrow)
	Ischaemic stroke	SMQ Ischaemic central nervous system vascular conditions (narrow)
	Stroke (broad)	SMQ Haemorrhagic central nervous system vascular conditions (narrow) OR SMQ Ischaemic central nervous system vascular conditions (narrow)
	MACE	Fatal events in SOC Cardiac OR  Fatal events in SOC Vascular OR  Any fatal or nonfatal events in SMQ Myocardial infarction (narrow) OR  PTs Cardiac death, Sudden death, Sudden Cardiac death OR  Any fatal or nonfatal events as defined in PV Endpoint Stroke PTs
	Cardiac failure	SMQ Cardiac failure (narrow)
	QT prolongation	SMQ Torsade de pointes/QT prolongation (narrow)
	Venous thromboembolism	SMQ Embolic and thrombotic events, venous (narrow)

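### The SAP's MACE display is built from reported terms, so a death that the committee adjudicates as cardiovascular but that was reported under another term has no stated route into it

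*Protocol*

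**What the plan says.** Protocol 3.1.1 gives the Adjudication Committee three groups of cases. The first is every death, whatever term was reported: "All death cases will be assessed (to evaluate the primary cause of death". The second is "all adverse events categorized as major adverse cardiovascular events (MACE". The third is all acute IPF exacerbations. The review is done "by an independent Adjudication Committee (AC), in a blinded manner before data base lock", so a primary cause for every death will exist at analysis. The detailed rules are kept elsewhere: "The tasks and responsibilities of the DMC and the AC will be specified in a charter".

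SAP Table 7.8.1:1 defines MACE by a list of alternative criteria, all based on how the event was reported and coded:

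- fatal events by system organ class, cardiac ("Fatal events in SOC Cardiac OR") or vascular;
- the narrow myocardial infarction query, fatal or not;
- three named death terms ("PTs Cardiac death, Sudden death, Sudden Cardiac death OR");
- a list of stroke terms, fatal or not.

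For the adjudicated presentation, SAP 7.8.1 says that "the number of treatment emergent MACE events will be displayed including result of adjudication", overall and by signs of right heart dysfunction. The section opens with the rule that "All analyses of AEs will be based on the number of patients with AEs and NOT on the number of AEs". It ends by planning frequencies and percentages of patients by arm for each safety topic in the table, and MACE is one of those topics.

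**The concern.** The committee makes two findings that bear on MACE: whether an event categorised as MACE is confirmed, and what each patient died of. The SAP says where the first is shown. Nothing in the visible text says where the second goes, and the MACE criteria do not refer to it.

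This matters in this population. Protocol 5.3.7 requires worsening of the underlying disease to be recorded as an adverse event, and Protocol 1.2.2 lists progression of IPF among the most common events in the earlier sildenafil trial in advanced IPF. A death can therefore readily be reported under the lung disease, and an independent review of cause is most informative for such deaths.

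Cardiovascular safety is also not incidental here. Safety is part of the primary objective (Protocol 2.2). Protocol 2.3 says it is unknown whether giving the two drugs together brings additional side effects. Protocol 1.2.1 reports a higher proportion of myocardial infarctions on nintedanib and asks for further observation. Global Amendment 2 added MACE to the committee's remit. The display at stake is the one a reader would use to judge MACE on the combination.

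**Working it through.** No figure in the plan needs reproducing. The check sets the adjudication scope against the display rule.

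**Inputs**

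| Item | Source | Content |
|---|---|---|
| Deaths adjudicated | Protocol 3.1.1 | All, for primary cause |
| MACE adjudicated | Protocol 3.1.1 | Events already categorised as MACE |
| MACE selection | SAP Table 7.8.1:1 | Reported and coded terms only |
| Adjudicated display | SAP 7.8.1 | The selected MACE, with the adjudication result |
| Display of deaths | SAP 7.8.1 | Patients with events leading to death; adjudicated cause not mentioned |

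**Step 1. Name the sets, in patients with treatment-emergent events.**

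- T: at least one event meeting the term-based MACE criteria.
- C: those in T whose MACE the committee confirms, so C is contained in T.
- D: those whose death the committee attributes to a cardiovascular primary cause.

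**Step 2. What the display covers.** It shows T and, through the adjudication result, C. Everything in it lies inside T.

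**Step 3. Can D extend beyond T?** Membership of T depends on reported terms. Membership of D depends on the committee's finding, which is made for all deaths. Take a patient whose only fatal event is coded to a respiratory or IPF-progression term, with no infarction or stroke reported, and whose adjudicated primary cause is cardiovascular. That patient is in D and not in T. The display as written omits the patients in D but outside T. Nothing in the criteria makes that group empty.

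**Step 4. How wide is the gap?** It is limited. Any fatal event coded as cardiac or vascular, any of the three named death terms, and any reported infarction or stroke already puts the patient in T. Only cardiovascular deaths with none of these fall outside.

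**Step 5. Size.** The number omitted in an arm is (deaths in the arm) × (share in D but outside T). The documents give neither factor, so the product cannot be derived, and it is zero if no such death occurs. The scale per case follows from the planned arm size: 1 / 125 = 0.008, or 0.8 percentage points per omitted patient.

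**The case against.** The strongest case against the point is that it argues from silence in a text with parts removed. Protocol 7.3.4 refers to a section 7.3.3 for key safety endpoints that is not in the public text. The SAP contents list goes from 7.5 to 7.8. The committee's charter is not available. An analysis of adjudicated cause of death could sit in any of these. That stands, and it makes the fix conditional. It does not remove the point, because the MACE selection rule is visible and complete as a list, and no item in it uses the adjudicated cause.

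It is also fair that no treatment-emergent death disappears. A fatal event is serious, so it counts in the on-treatment SAE endpoint and in the table of events leading to death. What can be missing is its classification as cardiovascular.

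Four stronger readings are tempting, and the documents do not support them:

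- A reader might infer that adjudication removes MACE, so that correction runs only downwards. The SAP shows the selected events together with the adjudication result. No visible rule drops unconfirmed events.
- A reader might infer that an adjudicated cardiovascular death can never be added anywhere. The missing sections and the charter prevent that conclusion.
- A reader might infer from the wording about the number of MACE events that a patient with two events is counted twice. The general rule in SAP 7.8.1 counts patients, and patient frequencies and percentages by safety topic are already planned. At most the wording is loose.
- A reader might infer that the omission shrinks any difference between the arms. Adding a few deaths could widen, narrow or reverse a small difference.

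**Conclusion.** The point holds as a gap in one descriptive safety display. As the visible text stands, SAP 7.8.1 selects MACE by reported terms, and a treatment-emergent death reported under another term but adjudicated as cardiovascular is not carried in, although the committee will have produced that finding before database lock.

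The size is unknown and may be zero. A range would need an assumed number of deaths and an assumed reclassification share, and the documents offer no anchor for either. Safety analyses are descriptive with no hypothesis testing, so the primary endpoint and the hierarchical tests are untouched.

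The conclusion rests on two assumptions: that no section outside the public text, and no charter provision, already makes the link; and that the committee's cause-of-death categories include a cardiovascular one. The change is worth making because the data will already exist and the cost is small.

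**What to change.** In SAP 7.8.1, next to the MACE definition:

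- Add a row, *patients with adjudicated MACE*: patients with a committee-confirmed MACE, plus patients with a treatment-emergent death whose adjudicated primary cause is cardiovascular, whatever term was reported. Use the committee's own cause category and the treatment-emergent window already in that section. Count each patient once.
- Show number and percentage of patients by arm, beside the term-based MACE count already planned for the safety topics.
- Show MACE that the committee did not confirm as unconfirmed, so that both counts can be reconciled.
- If the charter or a section not in the public text already provides this, replace the above with a cross-reference.

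The cost is one definition and one table row from data the committee already produces. The downside is that the adjudicated count may come out slightly higher than it would under term-based selection.

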3.2 DISCUSSION OF TRIAL DESIGN, INCLUDING THE CHOICE OF CONTROL GROUP(S)

In the STEP-IPF trial sildenafil has been shown to improve patient-relevant outcomes such as dyspnea and quality of life in patients with advanced lung function impairment at 12 weeks [R12-3686]. In order to confirm these findings and a potential added benefit of sildenafil when added to current standard of care, a double-blind, parallel group trial design was selected where half of the patients will be treated with sildenafil and half of the patients will be treated with placebo matching sildenafil. All patients will be treated with nintedanib as background therapy considered usual care in patients with IPF.

The randomized treatment period duration of 24 weeks is thought to be adequate to evaluate if the efficacy is maintained after the primary endpoint assessment at 12 weeks. In addition it is considered an appropriate treatment duration to allow the collection of safety and tolerability data of concomitant treatment of nintedanib and sildenafil, as well as collection of additional safety data for nintedanib monotherapy in a population with a more advanced lung function impairment in comparison to the population enrolled in the Phase II and III TOMORROW and INPULSIS[®] trials.

The frequency of visits will allow close monitoring of emergent adverse events as well as control of liver enzyme values consistent with the recommendations of the prescribing information of nintedanib.

To obtain further efficacy and safety information on the concomitant treatment of nintedanib and sildenafil, lung function tests, clinical laboratory tests and electrocardiograms will be performed. Data on discontinuations and death will be recorded.

3.3 SELECTION OF TRIAL POPULATION

A total of approximately 250 patients with an IPF diagnosis and advanced lung function impairment will be randomized. Approximately 80 sites are each expected to include approximately 3 patients.

A log of all patients enrolled into the trial (i.e. who have signed informed consent) will be maintained in the ISF at the investigational site irrespective of whether they have been treated with investigational drug or not.

3.3.1 Main diagnosis for trial entry

Any patients diagnosed with IPF and who comply with eligibility requirements may qualify for participation in the trial.

Please refer to [section 8.3.1](#) (Source Documents) for the documentation requirements pertaining to the in- and exclusion criteria.

3.3.2 Inclusion criteria

1. Written informed consent consistent with ICH-GCP and local laws, signed prior to any study procedures being performed (including any required washout);
2. Male or female patients aged ≥ 40 years at visit 1;
3. A clinical diagnosis of IPF within the last 6 years before visit 1, based upon the ATS/ERS/JRS/ALAT 2011 guideline [[P11-07084](#)];
4. Combination of high-resolution computed tomography (HRCT) pattern, and if available, surgical lung biopsy pattern consistent with a diagnosis of IPF (see [appendix 10.1](#)) as assessed by the investigator based on a HRCT scan performed within 18 months of visit 1;
5. DLCO (corrected for Hb) $\leq 35\%$ predicted of normal at visit 1¹.

3.3.3 Exclusion criteria

1. Previous enrolment in this trial;
2. ALT, AST > 1.5 fold upper limit of normal (ULN) at visit 1¹;
3. Total bilirubin > 1.5 fold ULN at visit 1¹;
4. Relevant airways obstruction (i.e. pre-bronchodilator FEV1/FVC < 0.7 at visit 1¹);
5. History of myocardial infarction within 6 months of visit 1 or unstable angina within 1 month of visit 1;
6. Bleeding Risk:
 - Known genetic predisposition to bleeding;
 - Patients who require fibrinolysis, full-dose therapeutic anticoagulation (e.g. vitamin K antagonists, direct thrombin inhibitors, heparin, hirudin, etc.) or high dose antiplatelet therapy²;
 - History of haemorrhagic central nervous system (CNS) event within 12 months prior to visit 1;
 - History of haemoptysis or haematuria, active gastro-intestinal bleeding or ulcers and/or major injury or surgery within 3 months prior to visit 1;
 - International normalised ratio (INR) > 2 at visit 1¹;
 - Prothrombin time (PT) and activated partial thromboplastin time (aPTT) $> 150\%$ of institutional ULN at visit 1¹;
7. Planned major³ surgery during the trial participation, including lung transplantation, major abdominal or major intestinal surgery;
8. History of thrombotic event (including stroke and transient ischemic attack) within 12 months of visit 1;

9. Creatinine clearance < 30 mL/min calculated by Cockcroft–Gault formula ([appendix 10.2](#)) at visit 1¹;
10. Presence of aortic stenosis (AS) per investigator judgement at visit 1;
11. Severe chronic heart failure: defined by left ventricular ejection fraction (EF) < 25% per investigator judgement at visit 1;
12. Presence of idiopathic hypertrophic subaortic stenosis (IHSS) per investigator judgement at visit 1;
13. Second-degree or third-degree atrioventricular (AV) block on electrocardiogram (ECG) per investigator judgement at visit 1;
14. Hypotension (systolic blood pressure [SBP] < 100 mm Hg or diastolic blood pressure [DBP] < 50 mm Hg) (symptomatic orthostatic hypotension) at visit 1;
15. Uncontrolled systemic hypertension (SBP > 180 mmHg or DBP > 100 mmHg) at visit 1¹;
16. Known penile deformities or conditions (e.g., sickle cell anemia, multiple myeloma, leukemia) that may predispose to priapism;
17. Retinitis pigmentosa;
18. History of vision loss;
19. History of nonarteritic ischemic optic neuropathy;
20. Veno-occlusive disease;
21. History of acute IPF exacerbation or respiratory infection within 8 weeks of visit 2.
22. Treatment with nitrates, n-acetylcysteine, pirfenidone, azathioprine, cyclophosphamide, cyclosporine, prednisone >15 mg daily or >30 mg every 2 days OR equivalent dose of other oral corticosteroids as well as any investigational drug within 4 weeks of visit 2;
23. Treatment with prostaglandins (e.g., epoprostenol, treprostinil), endothelin-1 antagonists (e.g., bosentan, sitaxsentan, ambrisentan), phosphodiesterase inhibitors (e.g., sildenafil, tadalafil, vardenafil) or a stimulator of guanylatcylase (e.g., riociguat) within 4 weeks of visit 2;
24. Treatment with potent CYP3A4 inhibitors such as ketoconazole, itraconazole and ritonavir within 4 weeks of visit 2;
25. Supplementation with L-arginine and concurrent use of grapefruit juice or St John's wort within 4 weeks of visit 2;
26. Treatment with the reduced dose of nintedanib (100 mg bid) within 4 weeks of visit 2⁴;
27. Permanent discontinuation of nintedanib in the past due to adverse events considered drug-related;
28. Known hypersensitivity or intolerance to nintedanib, sildenafil, galactose, peanut or soya or any other components of the study medication;

29. A disease or condition which in the opinion of the investigator may interfere with testing procedures or put the patient at risk when participating in this trial;
30. Alcohol or drug abuse which in the opinion of the treating physician would interfere with treatment;
31. Women who are pregnant, nursing, or who plan to become pregnant while in the trial;
32. Women of childbearing potential⁵ not willing or able to use highly effective methods of birth control per ICH M3 (R2) that result in a low failure rate of less than 1% per year when used consistently and correctly⁶;
33. Patients not able to understand and follow study procedures including completion of self-administered questionnaires without help.
34. Patients with underlying chronic liver disease (Child Pugh A, B or C hepatic impairment)

¹ Laboratory parameters, blood pressure and lung function tests may be re-tested within the permitted timeframe, if found abnormal at Visit 1 and thought to be a measurement error or was the result of a temporary and reversible medical condition.

² Exceptions: prophylactic low dose heparin or heparin flush as needed for maintenance of an indwelling intravenous device (e.g., enoxaparin 4000 IU subcutaneous (s.c.) per day) and prophylactic use of antiplatelet therapy (e.g., acetyl salicylic acid up to 325 mg/d, and/or clopidogrel at 75 mg/d, and/or equivalent doses of other antiplatelet therapy).

³ Definition of major is per investigator judgement.

⁴ Patients on treatment with nintedanib 150 mg bid during the screening period are eligible. However if an interruption or reduction of dose is required during the screening period or at time of randomization, the patient will no longer be eligible.

⁵ Women of childbearing potential are defined as: Any female who has experienced menarche and does not meet the criteria for "women not of childbearing potential" defined as: Women who are postmenopausal (12 months with no menses without an alternative medical cause) or who are permanently sterilized (e.g., tubal occlusion, hysterectomy, bilateral oophorectomy or bilateral salpingectomy).

⁶ A list of contraception methods meeting these criteria is provided in the patient information.

